Hypothesis 2: The effects of the intervention on oral hygiene outcomes (i.e., plaque index and gingival index) will be mediated by oral care self-efficacy, leadership self-efficacy, use of behaviors cueing, leadership focused communication.

Measures**Primary outcomes:**

1) Plaque index: UNC Modified Green and Vermillion Oral Hygiene Index. Plaque was measured as 0 = No plaque, 1 = Plaque covers $<1/3$ tooth, 2 = Plaque covers $\geq 1/3$ but $<2/3$ tooth and 3 = Plaque covers $\geq 2/3$ tooth. *The proportion of sites with plaque deposits on at least less than 1/3 of crown will be calculated for each participant for use in analyses.*

2) Gingival Index: UNC Modified Loe and Silness Gingival Index. Gingival inflammation is classified as 0 = Normal gingiva, 1 = Mild inflammation, no bleeding on probing, 2 = Moderate inflammation, bleeding on probing, 3 = Severe inflammation, tendency to spontaneous bleeding. *The proportion of sites with at least some mild inflammation will be calculated for each participant for use in analyses.*

Secondary outcomes:

Participant oral hygiene behavioral outcomes, note for outcomes with both participant and care-partner report, care-partner report will be used for all statistical analyses. Participant data will be presented descriptively by arm and time.

1) Participants' frequency toothbrushing (reported by participants and care-partners).

Numeric scale ranging from 1-6. Data will be dichotomized into the following categories: less than twice a day or twice a day or more. Care-partner response will be used for analysis.

2) Participants' duration of toothbrushing (reported by dental hygienist).

Ordinal measure, consisting of 3 response types (< 1min; ≥ 1 min & < 2min; ≥ 2 min). Data will be treated as ordinal.

For sensitivity analysis we will dichotomize responses into the following categories: < 2 min vs. 2 min or more.

3) Participants' frequency of interdental cleaning (reported by participants and care-partners).

Ordinal scale ranging from 1-6. Data will be treated as ordinal. For sensitivity analysis we will dichotomize responses into the following categories: < once per day or once per day or more. Care-partner response will be used for analysis.

4) Participants' interproximal cleaning technique (reported by dental hygienist).

Categorical measure, consisting of 4 response types. Responses will be dichotomized into the following categories: less than optimal or interproximal surfaces cleaned using 'c' shape.

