
Exploratory Analyses (Aim 2): If findings from the analyses outlined above, for the primary outcomes of plaque and gingival indices, indicate an overall intervention effect, we will consider exploratory mediation analysis. Specifically, if a significant effect of the two treatment packages is observed (relative to control), we will explore the extent to which the proposed mediators (oral care self-efficacy, leadership self-efficacy, use of behaviors-cueing, or leadership communication) mediate the effect of the two treatment packages compared to control on the primary outcomes (plaque and gingival indices). Given the available sample size, we will consider the mediators independently and estimate preliminary single mediation effects using causal mediation analysis. Model-based causal mediation involves a two-step process. First, we specify a mediator model to obtain the conditional distribution of the mediator given the exposure, and an outcome model to obtain the conditional distribution of the outcome given the exposure and mediator. Each model is fit separately and then their fitted objects are inputted into a mediation function, which estimates the effects of interest. The mediator model will be specified as a linear regression of the mediator at 3 months post-randomization on the exposure (treatment allocation) and baseline values of the mediator. The outcome model will be specified as a linear regression of the outcome at 6 months post-randomization on the mediator at baseline, and 3 months after randomization, and the exposure (randomization assignment). Using the mediator and outcome regression models we will estimate the corresponding preliminary indirect and direct effects for each mediator. Of particular interest to the present study are the preliminary indirect effect estimates, which measure the effect of the exposure (randomization assignment) on the outcome (plaque or gingival index) via the mediator of interest (e.g. oral care self-efficacy). We will estimate corresponding standard errors and 95% confidence intervals for these effects using bootstrapping.

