Should model diagnostics from our exploratory mediation analysis (e.g. RMSEA) indicate poor model fit or we observe indications of instability in effect estimates (e.g. wide confidence intervals), we will opt for a paired down assessment of potential mediators. In this paired down approach, we will explore changes in potential mediators following intervention (e.g. oral care self-efficacy) by summarizing mean change (6 months - baseline), (3 months - baseline) in potential mediators stratified by intervention group (**TG1, TG2, CG**). To inform future studies, we will calculate corresponding effect sizes (Cohen's d for independent samples) for key between-group differences (**TG1 vs. CG; TG2 vs. CG**) in mean change for potential mediators (e.g. oral care self-efficacy). These descriptive summaries will provide inputs to aid in powering a future mediation analysis to examine the underlying mechanisms of intervention effects.

Supplementary Strategies

Assessment of Modified Measures. For modified scales, which include the secondary outcome of oral care self-efficacy, and the exploratory mediators of adaptive leadership and focused communication, we will confirm unidimensionality via exploratory factor analysis, and subsequently compute Cronbach's alpha to examine reliability for each modified scale.

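### The SAP replaces the indirect-effect estimates if their confidence intervals look wide, but the width of an indirect-effect interval depends on the effect, so what is reported would depend on the result

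*Combined protocol and SAP*

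**What the plan says.** Hypothesis 2 (SAP, Study Aims) opens: "The effects of the intervention on oral hygiene outcomes (i.e., plaque index and gingival index) will be mediated by oral care self-efficacy", and goes on to name three further care-partner mediators. Under Exploratory Analyses (Aim 2) the analysis is conditional: "if a significant effect of the two treatment packages is observed (relative to control), we will explore the extent" of mediation. Because of the available sample size, "we will consider the mediators independently and estimate preliminary single mediation effects using causal mediation analysis".

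The mediator model is a "linear regression of the mediator at 3 months post-randomization on the exposure (treatment allocation) and baseline values of the mediator". The outcome model regresses the 6-month index on the baseline mediator, the 3-month mediator and arm. On precision the SAP says: "We will estimate corresponding standard errors and 95% confidence intervals for these effects using bootstrapping".

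The next paragraph gives two reasons to leave this analysis. One is poor fit by an index such as RMSEA, which is not considered here. The other is apparent instability, with wide intervals as the only example: if "we observe indications of instability in effect estimates (e.g. wide confidence intervals), we will opt for a paired down assessment of potential mediators". The replacement is a set of mean changes in the mediators by arm, with Cohen's d against control, meant to help power a later mediation study.

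**The concern.** The decision to show or withhold the indirect effects comes after they and their intervals are known, and it turns on a word that the SAP does not define. That would matter less if width measured only the quality of the data. For a product of two coefficients it does not: the standard error contains the coefficients themselves. A width rule therefore filters estimates partly by their own size, and the estimates that survive need not be centred on the truth.

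Two things are at stake. One is a fair account of Hypothesis 2. The other is the SAP's stated wish to inform a future mediation trial. The fallback describes only the mediators. It says nothing about the path from mediator to plaque or gingival index, which such a trial would need. Table 4 of the SAP already plans the mediators by arm and visit, so the switch gives up the indirect effects for little new information.

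The unit matters too. Four mediators and two indices give 4 × 2 = 8 pairs for each comparison with control, and the SAP does not say whether one wide interval moves that pair or all of them to the fallback.

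**Working it through.** The rule contains no figure to reproduce, so the check is of how it behaves.

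**Inputs from the documents.** Completers: 19 control, 18 TG1 and 17 TG2, 54 in all (SAP sample size table). The two regressions and bootstrap 95% intervals are those of Exploratory Analyses (Aim 2).

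**Assumptions, not in the documents.** Standardised variables; correlation 0.5 between baseline and 3-month mediator; path values a (TG2 versus control on the mediator) and b (mediator on the index) between 0 and 0.8; percentile bootstrap; every completer has both measurements; the switch is applied to each mediator separately; and the three cut-offs below. Most runs also set a direct effect of 0.5 and gave TG1 half the TG2 effect. Several independent runs were made (up to 2,000 trials per scenario, 300 to 400 resamples), and ranges below are across runs. The sign of b does not affect width.

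**Step 1: formula.** Var(ab) = a²·SE_b² + b²·SE_a² + SE_a²·SE_b², and width ≈ 3.92·√Var.

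- SE_a = √(1 − 0.5²) × √(1/17 + 1/19) = 0.866 × 0.334 = 0.289.
- SE_b = 1 / (0.866 × √50) = 0.163, where 50 is 54 less the four other coefficients.
- At (a, b) = (0, 0): 3.92 × 0.289 × 0.163 ≈ 0.185.
- At (0.5, 0.3): 3.92 × √(0.0067 + 0.0075 + 0.0022) = 0.50.
- At (0.8, 0.3): 3.92 × √(0.0171 + 0.0075 + 0.0022) = 0.64.
- At (0.8, 0.5): 3.92 × √(0.0171 + 0.0209 + 0.0022) = 0.79.
- At (0, 0.6), a null mediator: 3.92 × √(0 + 0.0301 + 0.0022) = 0.70.

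The simulated median widths, in the same order, are 0.29–0.31, 0.51–0.53, 0.63–0.66, 0.74–0.80 and 0.71. They agree with the formula except at (0, 0), where the bootstrap is wider because it is centred on estimated paths that are not exactly zero. Within the real-mediator scenarios, width and the absolute estimate correlate at 0.71 to 0.76.

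**Step 2: share of trials in which the estimate would be replaced.**

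| (a, b) | True ab | Width > 0.40 | Width > 0.70 | Width > 3 × absolute estimate |
|---|---|---|---|---|
| (0, 0) | 0 | about 20% | 0% | 99–100% |
| (0, 0.6) | 0 | 95–96% | 52% | 83% |
| (0.3, 0.3) | 0.09 | 67% | 10% | 84% |
| (0.5, 0.3) | 0.15 | 76–80% | 19% | 66–69% |
| (0.8, 0.5) | 0.40 | 98.5% | 67% | 18–20% |

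The 0.40 cut was chosen so that about 20% of the (0, 0) cases are replaced. On raw width, large real effects are replaced most often, but so is the one-path null (0, 0.6). On relative width the order largely reverses.

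**Step 3: mean of the estimates that are kept, at (0.8, 0.3), true ab = 0.8 × 0.3 = 0.24.**

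| Rule | Mean estimate |
|---|---|
| No rule | 0.22–0.24 |
| Keep if width ≤ 0.40 | about 0.06 |
| Keep if width ≤ 0.70 | 0.14–0.17 |
| Keep if width ≤ 3 × absolute estimate | 0.35–0.36 |

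At (0.5, 0.3), true ab 0.15, the relative rule moves the mean to 0.29. A raw cut biases the kept estimates towards zero and a relative cut biases them away from it.

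**The case against.** The strongest reply has three parts. First, the analysis is labelled exploratory and preliminary and runs only after an effect on the primary outcomes. With 54 completers against a target of 120, reluctance to present very imprecise mediation results is understandable. Second, the direction of any distortion depends on a scale that the SAP does not state. Third, the fallback drops no mediator: it summarises the potential mediators by arm, and Table 4 lists all four.

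All three stand as facts and limit the point. In particular, a reader might infer that the rule discards real mediators and keeps null ones. The documents do not support that. The SAP fixes no scale, and if width is judged against the estimate the pattern largely reverses. Even on raw width a null mediator with one strong path, such as (0, 0.6), is replaced more often than a real one at (0.5, 0.3). Such nulls are plausible here, since coaching may raise self-efficacy without changing plaque. The SAP also does not say that selection is made per mediator. Nor does it say that a narrow interval would be reported as absence of mediation.

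These arguments do not rescue the trigger. Moving to the relative reading changes the direction of the distortion and does not remove it. An undefined scale leaves that direction to a choice made after the results are seen. The exploratory label lowers the stakes, but it is not a reason to withhold estimates already computed.

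**Conclusion.** The concern holds in limited form. Wide intervals are an undefined, after-the-fact trigger, and because the width of a product's interval depends on the paths, acting on it makes reporting depend on the result. On the readings tested, a true indirect effect of 0.24 would be represented by retained estimates averaging anywhere from about 0.06 to about 0.35.

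These sizes rest on the assumed path values, the mediator correlation of 0.5, standardised scales, the chosen cut-offs and a switch made mediator by mediator. A switch for the whole analysis was not simulated, nor was the condition that a primary effect be found first. The dependence of width on the paths follows from the variance formula and needs none of the cut-offs. Severity is low: the analysis is exploratory and conditional, and the primary results are untouched.

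**What to change.** In the SAP's Exploratory Analyses (Aim 2), delete wide confidence intervals as a reason for replacing the mediation analysis. State that, once the condition for mediation is met, every planned indirect effect is reported with its bootstrap 95% interval whatever the width, labelled exploratory, with the descriptive mediator summary alongside and not in its place.

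If a feasibility rule is wanted, set it in advance on something that does not depend on the estimate. Examples are the number of dyads with both the 3-month mediator and the 6-month index, or the share of bootstrap resamples in which the models cannot be fitted. State whether the rule applies to each mediator or to the whole analysis.

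The cost is about a sentence of wording. The models are already fitted by the time the present rule would apply. The downside is that some wide exploratory intervals will be shown.

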1.3 SCHEDULE OF ACTIVITIES

Treatment Group 1

| Treatment Group 1 | Screening | Time 1 (Home Visit 1) Week 1: (within 42 days of screening) | Time 2 Week 4: (± 7 Days) | Time 3 Week 8: (± 7 Days) | Time 4 (Home Visit 2) Week 12: (± 14 Days) | Time 5 Week 16: (± 7 Days) | Time 6 Week 20: (± 7 Days) | Time 7 (Home Visit 3) Week 24: (± 14 Days) |
|-------------------------------------|-----------|--|---------------------------------|---------------------------------|---|----------------------------------|----------------------------------|---|
| Screen for eligibility | X | | | | | | | |
| Obtain verbal informed consent | X | | | | | | | |
| Schedule Visit 1 | X | | | | | | | |
| Obtain written informed consent | | X | | | | | | |
| Care Partner Questionnaire | | X | | | X | | | X |
| Study Participant Questionnaire | | X | | | X | | | X |
| Oral Health Evaluation | | X | | | X | | | X |
| ADCS-ADL | | X | | | | | | |
| Oral Hygiene Skill Assessment Sheet | | X | | | X | | | X |
| Coaching Module | | | | | | | | |
| Tailored Oral Hygiene Instruction | | | | | | | | |

| Treatment Group 1 | Screening | Time 1 (Home Visit 1) Week 1: (within 42 days of screening) | Time 2 Week 4: (± 7 Days) | Time 3 Week 8: (± 7 Days) | Time 4 (Home Visit 2) Week 12: (± 14 Days) | Time 5 Week 16: (± 7 Days) | Time 6 Week 20: (± 7 Days) | Time 7 (Home Visit 3) Week 24: (± 14 Days) |
|---|-----------|--|---------------------------------|---------------------------------|---|----------------------------------|----------------------------------|---|
| Montreal Cognitive Assessment (MoCA) | | X | | | X | | | X |
| Educational booklet provided | | X | | | | | | |
| Electronic Toothbrush Data Download | | | X | X | X | X | X | X |
| Detailed explanation of education booklet | | | | | | | | X |
| Exit Interview w/participant | | | | | | | | X |
| Exit Interview w/care partner | | | | | | | | X (via phone) |

Treatment Group 2

| Treatment Group 2 | Screening | Time 1 (Home Visit 1) Week 1: (within 42 days) | Time 2 Week 4: (± 7 Days) | Time 3 Week 8: (± 7 Days) | Time 4 (Home Visit 2) Week 12: (± 14 Days) | Time 5 Week 16: (± 7 Days) | Time 6 Week 20: (± 7 Days) | Time 7 (Home Visit 3) Week 24: (± 14 Days) |
|---------------------------------|-----------|---|---------------------------------|---------------------------------|---|----------------------------------|----------------------------------|---|
| Screen for eligibility | X | | | | | | | |

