4.4 END-OF-STUDY DEFINITION

A participant is considered to have completed the study if he or she has completed the baseline assessment, all 4 coaching modules (if applicable), the 3-month study visit, and the final 6-month study visit.

The end of the study is defined as completion of the 6-month follow up visit shown in the Schedule of Activities, Section 1.3.

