Clinical Oral Health Evaluation. (All groups) The hygienist performs an oral health evaluation (see detailed procedures in Section 8.1 Endpoint and other Non-Safety Assessments). The evaluation is used by the hygienist to guide tailored recommendations for the treatment plan for participants assigned to Treatment Group 2.

Assessment of technical and adaptive challenges and instruction. (Treatment Group 2) This assessment is completed in the location where the dyad normally does oral care, usually a bathroom with a large mirror over the sink. Because the interventionist and the care partner must integrate the tailored instruction, they both will observe. Standing in front of a mirror, the dental hygienist will ask the participant to brush using his/her normal toothbrush to assess the participant's toothbrushing technique and begin to identify technical challenges and areas for specific feedback on technique, including areas of the dentition missed in brushing. S/he will then demonstrate the proper technique on a mouth model using a smart electronic toothbrush. Standing in front of a mirror, participant will then be asked to brush her/his teeth again, using the smart electronic toothbrush and the technique demonstrated. This approach is based on the approach developed by others³² for the clinical setting and adapted for the in-home setting. We will recommend use of interdental cleaning aids. Using the same approach as above, the hygienist will assess interdental cleaning by participants and assess cleaning partial dentures, if applicable. The hygienist will demonstrate the correct cleaning techniques and ask the participant to return-demonstrate. The participant and care partner will then be shown how to use a disclosing tablet to identify areas of dentition missed in brushing. The care partner is given an electronic toothbrush to support the collaborative effort of the dyad in regular and appropriate oral hygiene behavior. The care partner is also asked to demonstrate use of the electronic toothbrush to ensure that s/he understands. The oral hygiene technique assessment will be conducted at each visit. Examples of technical challenges that might be identified include limited hand dexterity which will guide selection of the right tool for interdental cleaning, or gum conditions that might guide recommendations

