8 STUDY ASSESSMENTS AND PROCEDURES

8.1 ENDPOINT AND OTHER NON-SAFETY ASSESSMENTS

Screening

Telephone screening will be conducted to determine eligibility. The study coordinator will first confirm that both the participant and the care partner are interested in participating in the study. After obtaining permission from the participant to ask the care partner questions about the participant's health and every day activities, the care partner will then be asked questions about the functional abilities and health conditions of the potential participant to determine eligibility (See Oral Health Study Phone Screening Report Form). Preliminary eligibility will be determined by the study coordinator at the end of the call. The PI or designee at each site will then review the responses to the health conditions and determine final eligibility. The screening interview should occur within 42 days of enrollment.

Home Visits

The care partner and participant will complete the questionnaires in separate rooms from one another.

Participant Questionnaire:

- Sociodemographics (Baseline) for the study participant including date of birth, gender, years of education completed, race/ethnicity, marital status
- Oral Health Knowledge Scale: Our team has developed a 12-item oral health knowledge scale to assess the knowledge of oral self-care such as frequency and technique of brushing and flossing, duration of brushing, and tongue cleaning that are consistent with general recommendation by dental professionals.³⁷ Oral hygiene behavior (investigator developed) asks about participants' frequency of toothbrushing, flossing, and mouth rinse. The response categories will be coded as 1= Twice a day or more, 2=once a day, 3= Several times a week, 4= Once or less than once a week, 5=Hardly ever, and 6= Never. Geriatric Oral Health Assessment Index³⁸ asks 13 questions about self-perceived oral health. The response categories of each item range from 1=always, 2=sometimes, and 3=never. Xerostomia Inventory³⁹ asks 11 questions about the signs and severity of xerostomia⁸. The responses of each question range from 1=never, to 5=very often. PHQ-8⁴⁰ is an 8-item screen for depression that is administered to the participant.

Care Partner Questionnaire:

- Sociodemographics (Baseline) for the care partner including date of birth, gender, years of education completed, race/ethnicity, marital status, and medical and dental insurance for care partner and for the participant

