Electronic Toothbrush Data. The secondary outcomes of participants' frequency and duration of toothbrushing was also measured via electronic toothbrush for participants randomized to **TG1** or **TG2**, at baseline, 3 months and 6 months post-randomization. We anticipate a substantial proportion of participants may have missing data for frequency and duration of toothbrushing due to toothbrush device issues (e.g. battery, glitches etc.). Following the identification and removal of test cases in the dataset, we will examine outliers and missing data patterns via visualization to inform subsequent strategies. Our primary goal is to identify a subset of participants with complete data for frequency and duration of toothbrushing in the electronic toothbrush dataset. These data will be used as a validation set to examine agreement between participant self-report, care-partner report, and electronic toothbrush-assessed frequency and duration of toothbrushing. To align with the care-partner and participant reported toothbrushing data, we will calculate an average measure for frequency and duration based on 6 days of consecutive or non-consecutive data, surrounding the baseline, 3 month, and 6 month assessment date, which will serve as the index date for each visit. Lastly, we will compute relevant interclass correlation coefficients to explore agreement between participant self-report, care-partner report, and electronic toothbrush assessed frequency and duration of toothbrushing.

Descriptive Tables

Table 1. Participant demographics by arm at baseline.

- Variables for inclusion: age, sex, education, race, oral health knowledge score, ADL score, MOCA score

Table 2. Care-partner demographics by arm at baseline.

- Variables for inclusion: age, sex, education, race, oral health knowledge score

Table 3. Primary and secondary outcomes by arm at baseline, 3 months, and 6 months.

- Variables for inclusion: frequency toothbrushing, duration of toothbrushing, frequency of interdental cleaning, interproximal cleaning technique, oral hygiene skills score, oral health knowledge score.
- *Participant oral health knowledge score (separately – not a secondary outcome).*

Table 4. Exploratory mediators by arm, at baseline, 3 months, and 6 months.

- Variables for inclusion: oral care self-efficacy, leadership self-efficacy, behaviors cueing methods, leadership focused communication.

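### The baseline device window can hold only days after the smart brush was supplied, so the baseline agreement coefficient mixes reporting error with behaviour change

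*Combined protocol and SAP*

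**What the plan says.** The SAP (Supplementary Strategies, Electronic Toothbrush Data) treats brush-recorded frequency and duration in Treatment Groups 1 and 2 as measured at baseline, 3 months and 6 months, and plans to use participants with complete recordings as a validation set. The purpose of the averaging window is stated: "To align with the care-partner and participant reported toothbrushing data". The window is "based on 6 days of consecutive or non-consecutive data, surrounding the baseline, 3 month, and 6 month assessment date", with each visit date as the index date. No before/after split and no maximum distance from the visit are given. The statistic is stated as follows: "we will compute relevant interclass correlation coefficients to explore agreement between participant self-report, care-partner report, and electronic toothbrush assessed frequency and duration".

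The protocol fixes the timing around that window.

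- **Downloads.** Section 1.3 leaves screening and Time 1 blank and marks Weeks 4, 8, 12, 16, 20 and 24: "Electronic Toothbrush Data Download | | | X | X | X | X | X | X". The row is the same in both treatment groups.
- **Order within a visit.** Section 8.1 places the hygienist's part after both questionnaires. The participant questionnaire "asks about participants' frequency of toothbrushing, flossing, and mouth rinse".
- **Supply of the brush.** Section 10.1.1.1 requires written consent before the intervention starts, and Section 1.3 places that consent at Home Visit 1. In Treatment Group 2 the hygienist first watches brushing with the usual brush; then the "participant will then be asked to brush her/his teeth again, using the smart electronic toothbrush and the technique demonstrated" (Section 6.1.1).
- **Last contact.** "The end of the study is defined as completion of the 6-month follow up visit" (Section 4.4).

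**The concern.** A validation of reported against recorded brushing needs both to describe the same period. At baseline they cannot. The report is given before the smart brush is in use, and every recorded day comes afterwards. Section 4.2 raises the possibility that the brush is itself an active ingredient, and Treatment Group 2 also receives its first coaching module at that visit (Section 4.1). The trial is designed to change brushing between the two periods being compared.

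A low baseline coefficient could then be read as poor reporting when part of it is the behaviour change under study. This matters for interpretation because care-partner report is the analysed source for brushing frequency, a secondary outcome. The distortion may also differ by arm, since only Treatment Group 2 is coached.

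**Working it through.** The plan gives no figure to reproduce. The check is one of timing, followed by illustrations of direction.

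**Step 1: where the six days can fall relative to the report**

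| Visit | Scheduled downloads around it | Days before | Days after |
|---|---|---|---|
| Baseline (Home Visit 1) | none at the visit; first at Week 4 | 0 | 6 |
| 3 months (Home Visit 2) | Weeks 8, 12 and 16 | anywhere from 0 to 6 | the remainder |
| 6 months (Home Visit 3) | Weeks 20 and 24; none later | 6 | 0 |

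The baseline row follows from consent, supply and download timing. Section 9.1 is consistent with it: the duration hypothesis starts its series in Week 1 of the intervention, not before it. At 3 months, data can exist on both sides. For Treatment Group 2, later days follow coaching module 4 and tailored instruction. For Treatment Group 1, Section 1.3 schedules neither at that visit.

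**Step 2: effect on an ICC with error-free instruments**

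The documents give no standard deviation, shift or correlation, so these are assumptions. Let the report equal the pre-visit level (variance 1). Let the device average have share w = k/6 of its days after the visit, with pre/post correlation r and mean shift d in SD units. Then:

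- Var(device) = (1 − w)² + w² + 2w(1 − w)r
- Cov = (1 − w) + wr
- ICC (absolute agreement) = Cov / [(1 + Var(device))/2 + (wd)²/2]

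With r = 0.8 and d = 0.5:

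- k = 6 (baseline): 0.8 / (1 + 0.125) = 0.71
- k = 3 (one possible 3-month split): 0.9 / (0.95 + 0.03125) = 0.92
- k = 0 (6 months): 1.00

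Over r from 0.6 to 1.0 and d from 0 to 1.0, the range is 0.40 to 1.00 at k = 6 and 0.78 to 1.00 at k = 3. The SAP does not say which form of ICC it means. Ignoring the mean shift (d = 0) does not remove the effect: at k = 6 the value is still 0.80 for r = 0.8 and 0.60 for r = 0.6.

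**Step 3: effect on the dichotomised frequency**

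The SAP dichotomises frequency at twice a day. Take p = 0.36 reporting twice a day (Section 2.1, the team's previous study of people with cognitive impairment). Assume a share s of the rest move to twice a day on receiving the brush, nobody moves down, and reports are error-free.

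- Device margin = p + (1 − p)s
- Observed agreement = p + (1 − p)(1 − s)
- Chance agreement comes from the two margins

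For s = 0.25 the device margin is 0.52 and observed agreement is 0.84. Chance agreement is 0.36 × 0.52 + 0.64 × 0.48 = 0.4944, so kappa = (0.84 − 0.4944)/(1 − 0.4944) = 0.68. For s = 0.10, 0.50 and 0.75, kappa is 0.87, 0.42 and 0.19. Kappa is not the SAP's statistic; this shows only that the direction is the same on the dichotomised scale.

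**The case against.** Several objections stand and limit the point.

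- **The analysis is exploratory.** The secondary brushing outcomes use care-partner report for frequency and hygienist report for duration, so nothing formal rests on this window.
- **No trend is planned.** A reader might infer that the SAP intends to show reporting improving from baseline to 6 months. It names no comparison of agreement across visits. The trend problem arises only if coefficients are set side by side or pooled.
- **The 3-month split is unknown.** A reader might take the window to be half before and half after the visit. The SAP does not say so, and the split could differ by participant.
- **The 3-month mechanism is specific to one arm.** It is tempting to say that reported and recorded periods match only at 6 months. With no coaching or tailored instruction at Home Visit 2, days after that visit in Treatment Group 1 may still represent the reported habit.
- **The recall period is not stated.** The response categories read as usual habit. The quoted questionnaire item covers frequency only, so the argument is not shown for reported duration.

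None of this rescues baseline. Whatever the recall period, a report of usual frequency given before the brush is supplied cannot describe days after it.

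**Conclusion.** The baseline comparison does not measure agreement as written and should be changed. This rests on the schedule and the order of procedures alone. The 3-month part is weaker: an unspecified window that may include days after the report and, in Treatment Group 2 only, days after further coaching and instruction. At 6 months the window precedes the report under the download schedule.

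The size of the distortion cannot be derived from the documents. The ICC and kappa values show direction under assumed shifts, correlations, move shares and error-free reports; they do not estimate what this trial will see. Nor do the documents support reading all baseline disagreement as behaviour change. Misreporting may contribute too, and the two cannot be separated. The primary plaque and gingival analyses and the secondary tests are unaffected.

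**What to change.** Amend the SAP paragraph as follows.

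1. Run the agreement analysis at 3 and 6 months only.
2. At each, average six available days, consecutive or not, before the visit date and within a stated maximum distance from it.
3. Report the days after Home Visit 1 separately by arm, as data from the first week after the brush was supplied, and do not compare them with the baseline questionnaire.

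This needs no new data collection. It gives up one nominal agreement time point, and participants without enough pre-visit days drop out. A stricter rule of six consecutive calendar days is unnecessary. The SAP already expects substantial missing device data, and the sample-size table dated 05/08/24 shows only 18 + 17 = 35 completers in the two brush arms.

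One check should come before the maximum distance is set. Section 4.1 gives about 15 days of storage per brush, while Weeks 8 to 12 and 20 to 24 are nominally 28 days apart. It does not say which days survive when memory fills, or whether the storage of the two brushes adds up. If a single brush stopped recording when full, the last 28 − 15 = 13 days before the visit would be missing. If it overwrote the oldest days, the pre-visit days would be kept, but from Home Visit 1 (Week 1) to Week 4 the first 21 − 15 = 6 days would be lost. The post-Visit-1 data should therefore be labelled by their actual dates.
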